7.2.7 Incidence of IRIS

Endpoints

The endpoint is the first occurrence of IRIS over the 48-week visit. IRIS diagnosed at baseline will not be considered in the analysis.

Descriptive statistics and graphical representation

The analyses will be performed with the mITT population and DPS1. Data will be summarized with the number and percentage of participants with an IRIS. Kaplan-Meier curves will also be plotted.

Statistical methodology

The incidence of IRIS will be estimated with the Kaplan-Meier method. The follow-up will begin at baseline (date of study treatment initiation) and continue until the week 48 visit, study discontinuation or death, loss to follow-up, or onset of IRIS; whichever occurs first.

The effect of study treatment will be assessed using Cox regression model with treatment group and adjustments for stratification factor (country/group of neighbouring countries and baseline CD4 cell counts (<50 or $\geq 50/\mu\text{L}$)). An adjusted hazard ratio (HR) and the associated 95% Confidence Interval (CI) will be calculated.

7.2.8 Incidence of hospitalisation

Endpoints

The endpoint is the first occurrence of hospitalisation over the 48-week visit. Hospitalisation occurring before the initiation of study treatment (baseline) will not be considered in the analysis.

Descriptive statistics and graphical representation

The analyses will be performed with the mITT population and DPS1. Data will be summarized with the number and percentage of hospitalised participants. The Kaplan-Meier curves will also be plotted.

Statistical methodology

The incidence of hospitalisation will be estimated with the Kaplan-Meier method. The follow-up will begin at baseline (date of study treatment initiation) and continue until the week 48 visit, study discontinuation or death, loss to follow-up, or hospitalisation; whichever occurs first.

The effect of study treatment will be assessed using Cox regression model with treatment group and adjustments for stratification factor (country/group of neighbouring countries and baseline CD4 cell counts (<50 or $\geq 50/\mu\text{L}$)). An adjusted hazard ratio (HR) and the associated 95% Confidence Interval (CI) will be calculated.

7.2.9 Duration of hospitalisation

Endpoints

The endpoint is the duration of the hospitalisation during the 48-week period. The event of interest is the occurrence of last discharge (end date of hospitalisation) from hospital. A transfer to a palliative care will not be considered a discharge. Hospitalisation occurring before the initiation of study treatment (baseline) will not be considered in the analysis.

Descriptive statistics and graphical representation

The analyses will be performed with the hospitalised patients in the mITT population and DPS1. Data will be summarized with the number and percentage of participants discharged from hospital, and the median (95% CI) duration of hospitalisation. The Kaplan-Meier curves will also be plotted.

Statistical methodology

The proportion of participants discharged from hospital and the median duration of hospitalisation will be estimated using the Kaplan-Meier method. Follow-up will begin at the date of first hospitalisation and continue until the week 48 visit, study discontinuation or death, loss to follow-up, or last discharge from hospital; whichever occurs first.

The effect of study treatment will be assessed using Cox regression model with treatment group and adjustments for stratification factor (country/group of neighbouring countries and baseline CD4 cell counts (<50 or $\geq 50/\mu\text{L}$)). An adjusted hazard ratio (HR) and the associated 95% Confidence Interval (CI) will be calculated.

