9.3.3 Secondary outcome analysis

All secondary outcome analysis will be done with the ITT population. The p-values will be two-tailed, with a significant level of 0.05.

The proportion of patients with HIV-ribonucleic acid (RNA) viral load <50 copies/mL at week 48 will be analysed using the snapshot approach. Fisher's exact test will be used to compare the estimated proportion between the two groups.

A genotypic resistance test will be performed in all patients with virological failure. Drugs resistance mutations will be identified from the International AIDS Society (IAS)-USA resistance testing panel (last version at the time of analysis) and for BIC we will use IAS, Agence Nationale de Recherches sur le SIDA (National Agency for AIDS Research) (ANRS) or Royal College of Physicians (RCP) lists to perform the analysis whenever they will be made available. Resistance to BIC will also be identified using phenotypic resistance test. Fisher's exact test will be used to compare the presence of at least one drug resistance mutation between the 2 groups.

The median time to reach CD4 cell count >200/ μ l will be estimated using the Kaplan-Meier method, censoring at week 48 or last follow-up date if not seen at week 48. Time to reach CD4 cell count >200/ μ l will be defined as the time between the date of study treatment initiation (baseline, week 0) and the date of which patient reached CD4>200/ μ l. The log-rank test will be used to compare the two survival functions. The p-values will be two-tailed, with a significant level of 0.05. The proportion of patients with CD4 cell count <350/ μ l at week 48 will be done with the ITT population, with the last observation carried forward (LOCF) approach. Fisher's exact test will be used to compare the 2 groups.

The median change in CD4/CD8 ratio from baseline to week 48 will be analysed with the ITT population, with the LOCF approach. The non-parametric Mann Whitney test will be used to compare the change from baseline between the 2 groups.

The incidence of IRIS will be analysed with the Kaplan-Meier method. The Log-rank test will be used to compare the two survival functions. The effect of study treatment on IRIS will be assessed using Cox regression model with treatment group and adjustments for stratification factors.

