The incidence of hospitalisation will be estimated by the Kaplan-Meier estimate. The Log-rank test will be used to compare the two survival functions. The duration of hospitalisation will be estimated by the cumulative days of hospitalisation during the course of study and will be compared between the 2 groups by using the Mann-Whitney test. The rate of relapse/recurrence will be estimated by the number of patients with relapse/recurrence divided by the total number patients in ITT population. Fisher's exact test will be used to compare the 2 groups.

The frequency of each Grade 2, 3 or 4 AEs, laboratory toxicities, and ART and OI/BI treatment changes and dose modifications due to toxicities and IRIS will be described and compared by group. Fisher's exact test will be used to compare the 2 groups.

The proportion of patients with health care resource use, and emergency room visits will be compared in the two groups with Fisher's exact test. The total inpatient days will be estimated by the cumulative inpatient days during the course of study and will be compared between the 2 groups by using the Mann-Whitney test.

To assess the impact of study treatment on the evolution of QOL at week 48, we will use multiple imputation approach to replace missing values. We will compare the treatment effect on QOL on each of the 5 datasets generated, including the imputed values, and the results will be combined with Rubin's rules. A generalized estimating equation (GEE) model will be used.

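### SAP 7.2.9 replaces the protocol's cumulative inpatient days in all participants with time from first admission to last discharge in hospitalised patients only, and no SAP analysis compares inpatient days

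*Combined protocol and SAP*

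**What the plan says.** Protocol 9.3.3, in the same words in v1.5 and v5.0, sets the population: "All secondary outcome analysis will be done with the ITT population". It then sets the measure: "The duration of hospitalisation will be estimated by the cumulative days of hospitalisation during the course of study". The inpatient component of health care resource use has a parallel rule: "The total inpatient days will be estimated by the cumulative inpatient days during the course of study". Both day counts are compared by Mann-Whitney test.

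SAP v0.3, section 7.2.9, differs on four points.

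- Population: "The analyses will be performed with the hospitalised patients in the mITT population and DPS1".
- Time origin: "Follow-up will begin at the date of first hospitalisation and continue until the week 48 visit".
- Event: "The event of interest is the occurrence of last discharge (end date of hospitalisation) from hospital".
- End of follow-up: apart from the week 48 visit, "study discontinuation or death, loss to follow-up, or last discharge from hospital; whichever occurs first".

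The result is a Kaplan-Meier median and an adjusted Cox hazard ratio, shown in Table 4. SAP 2.2.2 still lists total inpatient days within health care resource use. However, SAP 10.1.2 defines that endpoint as a proportion of patients, analysed by logistic regression, and Table 8 repeats this. SAP 7.2.8 analyses incidence separately in the full mITT population: "The endpoint is the first occurrence of hospitalisation over the 48-week visit".

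**The concern.** The two documents measure different things, and SAP 7.2.9 gives no reason for the change. Three features of its definition matter.

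1. For anyone admitted twice or more, the clock keeps running at home between stays.
2. Being admitted after baseline is itself an outcome. Restricting to admitted patients gives up the randomised comparison. A regimen that prevents short stays leaves longer ones behind, so it looks worse on duration although it has fewer admissions and fewer days in hospital.
3. A patient who dies in hospital is treated as if discharge could still have followed.

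At stake are the duration part of one secondary endpoint and the inpatient-days part of another. Neither would be reported as the protocol defines it, and the reported hazard ratio could point the opposite way from SAP 7.2.8.

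**Working it through.** **Population labels.** The protocol's ITT set (randomised and treated at least once) is the same as the SAP's mITT set. The difference is the restriction to hospitalised patients, not the label.

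**Inputs.** The documents give no figure for this endpoint, so there is none to reproduce. They give 220 per arm; every admission rate, stay length and gap below is an assumption.

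**Gap between stays.** SAP duration = stay 1 + gap + stay 2; protocol duration = stay 1 + stay 2. For two 3-day stays the protocol count is 3 + 3 = 6 days. With gaps of 7, 30, 90 and 263 days the SAP count is 3 + gap + 3 = 13, 36, 96 and 269 days. With one stay the two agree.

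**Effect on the median.** Simulated stays are lognormal with median 7 days and sigma 0.8, with a 90-day gap for those readmitted:

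| Readmitted | SAP median (days) | Actual inpatient days, median |
|---|---|---|
| 10% | 7.8 | 7.6 |
| 20% | 9.0 | 8.4 |
| 30% | 11.0 | 9.3 |
| 40% | 15.2 | 10.2 |

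With 10% against 30% readmission by arm, the discharge hazard ratio is about 0.66 on the SAP definition and about 0.83 on actual days. With 10% against 15% it is about 0.89 and 0.95. With 20% in both arms it is about 1 on either.

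**Selection.** Arm X has 24 stays of 3 days and 16 of 20 days: 24 × 3 + 16 × 20 = 392 days. Arm Y is the same but prevents k of the short stays, so its total is 392 − 3k. The hazard ratio is Y against X from a Cox model with Efron ties; below 1 means slower discharge. The Mann-Whitney test uses all 220 per arm, with zeros.

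| k | Admitted, Y (X: 40) | Days, Y (X: 392) | Median, Y (X: 3) | SAP 7.2.9 HR (95% CI) | Mann-Whitney p, favouring Y |
|---|---|---|---|---|---|
| 6 | 34 | 374 | 3 | 0.90 (0.57–1.43) | 0.48 |
| 12 | 28 | 356 | 20 | 0.79 (0.49–1.28) | 0.14 |
| 18 | 22 | 338 | 20 | 0.65 (0.39–1.10) | 0.023 |
| 24 | 16 | 320 | 20 | 0.49 (0.28–0.89) | 0.0015 |

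Y is better on admissions and days in every row and worse on the SAP hazard ratio in every row. If Y instead prevented half of each kind of stay, it would have 12 × 3 + 8 × 20 = 196 days with the same mix of lengths, and the hazard ratio would be 1. That is no reversal, but the halved burden would not show either.

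**What the restricted set cannot see.** In 2,000 simulated trials, stay lengths had the same distribution in both arms (single stays, mean about 8 days) and 20% against 30% were hospitalised. Mann-Whitney at two-sided 0.05 rejected in 69% of trials on all patients and in 5% on hospitalised patients only.

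**Death.** Of 40 admitted, let d die on day 5 (censored) and the rest be discharged on day 7. All 40 − d still at risk are discharged, so Kaplan-Meier gives 100% discharged. The actual share is (40 − d)/40 = 95%, 90% or 80% for d = 2, 4 or 8.

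**Is the day count compared anywhere else?** SAP 10.1.2 and Table 8 mention total inpatient days, but only inside a yes/no proportion with an odds ratio. Table 4 gives the Kaplan-Meier median. No section or table shell sums days per participant and compares the sums.

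**The case against.** - **Extent.** Duration is one part of a combined secondary endpoint whose other parts, incidence and relapse, are analysed in SAP 7.2.8 and 7.2.10. The cumulative-days rule appears only in the protocol's analysis section, not in the endpoint list. This is true and limits the reach. But the SAP itself treats duration as an endpoint, and the protocol's only definition of it is cumulative days.
- **Inpatient days are mentioned.** SAP 10.1.2 could be read as intending a descriptive summary of days. Even so, no between-arm comparison of days is specified.
- **Dates.** Protocol v5.0 (11 March 2024) is later than SAP v0.3 (22 November 2023), but its listed change is to data protection, so it is weak evidence that the sponsor reconsidered the analysis. This stands. The point rests on the mismatch and on the absence of any listed amendment to 9.3.3, not on date order.
- **Constructed examples.** The selection case prevents only short stays, and only its most extreme row has an interval excluding 1. The gap effect is small unless readmission is common or differs between arms. The death example puts every death before every discharge. All of this stands: reversal is a possibility, not a prediction.
- **The remedy.** With many zeros, Mann-Whitney nearly duplicates a comparison of who was admitted: in the selection example a chi-square test on admission gives p = 0.44, 0.11, 0.014 and 0.0006. Early death also produces few inpatient days. Both points are fair, and are reasons to add mean days and show deaths alongside. They do not support the SAP's clock.

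**Conclusion.** The concern holds. SAP 7.2.9 departs from protocol 9.3.3 in measure, population and method, without explanation, and no SAP analysis compares inpatient days between arms. The textual conflict needs no assumptions; the sizes do. The distortion from gaps is slight at low, equal readmission (7.8 against 7.6 days at 10%) and material if readmission is frequent or differs by arm. The selection effect depends on which stays are prevented: none if prevention is proportional across lengths, and a hazard ratio as low as 0.49 for the arm with fewer days if only short stays are prevented. The primary analysis and SAP 7.2.8 are untouched. This should be corrected before the SAP is signed.

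**What to change.** In SAP 7.2.9 and 10.1.2 and Tables 4 and 8:

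- Define the measure as cumulative inpatient days per participant from baseline to week 48, death or last observation, with zero if never admitted, in the whole mITT population.
- Compare the arms by one test, the protocol's Mann-Whitney test.
- Report length of stay per admission among hospitalised patients descriptively, without a hazard ratio.
- Keep the SAP's rule that transfer to palliative care is not a discharge, and state whether those days count as inpatient days.

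Inexpensive additions that answer the objections about zeros and early death are mean inpatient days per participant by arm with a bootstrap 95% confidence interval, one sensitivity analysis of inpatient days per 100 days of follow-up, and deaths by arm beside the result.

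If the sponsor prefers the SAP's definition, it should justify it and consider whether protocol 9.8 requires an amendment.

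The cost is SAP wording, two table shells and a small derivation. SAP 5.1 already allows updating before sign-off, and participants are not affected. The change assumes that start and end dates are recorded for every admission. The documents do not say so directly, but the protocol's endpoint requires it.

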8 PHARMACOVIGILANCE

8.1 Definitions

Term	Definition
Adverse Event (AE)	Any untoward medical occurrence in a participant to whom a medicinal product has been administered, including occurrences which are not necessarily caused by or related to that product.
Adverse Reaction (AR)	An untoward and unintended response in a participant to an investigational medicinal product which is related to any dose administered to that participant. The phrase "response to an investigational medicinal product" means that a causal relationship between a trial medication and an AE is at least a reasonable possibility, i.e. the relationship cannot be ruled out. All cases judged by either the reporting medically qualified professional or the Sponsor as having a reasonable suspected causal relationship to the trial medication qualify as ARs.
Serious Adverse Event (SAE)	An SAE is any untoward medical occurrence that: 
 • results in death • is life-threatening • requires inpatient hospitalisation or prolongation of existing hospitalisation • results in persistent or significant disability/incapacity • consists of a congenital anomaly or birth defect Other 'important medical events' may also be considered serious if they jeopardise the participant or require an intervention to prevent one of the above consequences. NOTE: The term "life-threatening" in the definition of "serious" refers to an event in which the participant was at risk of death at the time of the event; it does not refer to an event which hypothetically might have caused death if it were more severe.
Serious Adverse Reaction (SAR)	An AE that is both serious and, in the opinion of the reporting Investigator, believed with reasonable probability to be due to one of the trial treatments, based on the information provided.
Suspected Unexpected Serious Adverse Reaction (SUSAR)	
 • A SAR, the nature and severity of which is not consistent with the information about the medicinal product set out in section 4.8 "Undesirable Effect" of the SmPC

"Severe" is often used to describe intensity of a specific event, which may be of relatively minor medical significance. "Seriousness" is the regulatory definition supplied above.

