9.2 Planned recruitment rate

In the ANRS 146 OPTIMAL trial, in which similar patients were enrolled (late presenters with low CD4 cell count or ADE), 10% of screened patients were not eligible. Based on this information, we estimated that about 489 patients should be screened. Centres of NEAT ID Network with infectious disease units for inpatient and outpatient care will be the prioritised study sites of the LAPTOP Trial. We expect that about 45 sites in total across eight European countries. Therefore, we estimated that about 7-15 patients should be screened per site.

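### SAP 7.2.9 has no rule for a hospital stay already running at first dose, and its measure of duration departs from the protocol's cumulative inpatient days

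*Combined protocol and SAP*

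**What the plan says.** **SAP 7.2.9.** The endpoint is set out as "The endpoint is the duration of the hospitalisation during the 48-week period", and the event is the last discharge. On the analysis set: "The analyses will be performed with the hospitalised patients in the mITT population and DPS1". On the clock: "Follow-up will begin at the date of first hospitalisation and continue until the week 48 visit", or until study discontinuation, death, loss to follow-up or last discharge if earlier. The summary is a Kaplan-Meier median and the comparison is an adjusted Cox model. The exclusion reads: "Hospitalisation occurring before the initiation of study treatment (baseline) will not be considered in the analysis".

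**SAP 7.2.8.** The companion endpoint carries the same exclusion sentence, directly after "The endpoint is the first occurrence of hospitalisation over the 48-week visit".

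**Protocol v5.0, 9.3.3** (same wording in v1.5). "The duration of hospitalisation will be estimated by the cumulative days of hospitalisation during the course of study", with a Mann-Whitney comparison. All secondary outcomes are to be analysed in the ITT population, defined as everyone randomised who took study treatment at least once. That is the membership of the SAP's mITT set. No exclusion for earlier stays is stated.

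**SAP 10.1.2.** Total inpatient days to week 48 appear under health care resource use without the exclusion, but the model is a logistic regression on a proportion of patients.

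**SAP 3.2.** Randomisation takes place on the day treatment starts, so day 0 below is both.

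**The concern.** A patient who takes the first dose in a hospital bed has a stay lying partly before and partly after randomisation. The later part is outcome data: it is when recovery, IRIS or interactions with infection treatment could lengthen or shorten the admission. SAP 7.2.9 does not say whether that part counts, and one natural reading discards it.

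Such patients are plausible here. Eligibility (protocol v5.0, 5.1) covers AIDS, opportunistic infection under treatment, and severe bacterial infection, for which an unscheduled admission is one of the qualifying features. Section 9.2 adds: "Centres of NEAT ID Network with infectious disease units for inpatient and outpatient care will be the prioritised study sites".

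At stake is whether the reported duration matches the protocol's definition, and whether two programmers working from the same text would get the same answer.

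**Working it through.** The documents give no figure for inpatients at first dose, length of stay or days lost, so there is no plan figure to reproduce. The check compares the texts and then applies each reading to assumed patients.

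**1. How the exclusion sentence is used elsewhere.** In SAP 7.2.8 it qualifies a first occurrence, so it works as an onset rule. SAP section 8 uses the same form of words for adverse events, and SAP 7.1 and 7.2.7 set aside events already diagnosed at baseline. The pattern is exclusion by when an event began. Against that, the 7.2.9 endpoint is confined to the 48-week period, which also fits removing only hospital time before day 0.

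**2. What the clock does.** It starts on the date of first hospitalisation. For someone already in hospital that date precedes day 0, and no day-0 start is supplied. Under the onset reading the clock moves to the next admission. If there is none, the patient is not in the hospitalised set.

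**3. Assumed patients.** Dates are invented for illustration, with day 0 = first dose. The SAP clock is last discharge minus first counted admission. The protocol measure is the sum of days per stay, taking the course of the study to start at day 0, which the protocol does not spell out.

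| Stays (days) | Onset reading, SAP clock | Cut at day 0, SAP clock | Clock from true admission | Cumulative days from day 0 |
|---|---|---|---|---|
| -10 to 15 | not in analysis | 15 - 0 = 15 | 15 + 10 = 25 | 15 |
| -10 to 15; 100 to 105 | 105 - 100 = 5 | 105 - 0 = 105 | 105 + 10 = 115 | 15 + 5 = 20 |
| -10 to -2; 100 to 105 | 5 | 5 | 5 | 5 |

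The third row shows that a stay finished before day 0 causes no difficulty. The disagreement comes from stays that span day 0.

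The second row shows a further departure. With the stay cut at day 0, the SAP clock gives 105 days where the patient spent 20 in hospital; the other 105 - 20 = 85 are the days at home between day 15 and day 100. Protocol 9.3.3 would not count those.

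**4. Whether another analysis fills the gap.** SAP 10.1.2 has no exclusion, but its model compares the proportion of patients using resources. No SAP model compares the number of inpatient days between arms.

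**The case against.** The strongest reply is that the SAP never says an ongoing stay is dropped whole. That stands. A reader might infer such a rule from 7.2.8, and it is the more natural reading, but the 48-week wording and the protocol's cumulative days both allow the post-dose days to count. The defect is a missing rule, not a stated one.

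Other points on that side also stand:

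- SAP 7.2.8 is not in error. It is time to first event from baseline, and a stay already running at time zero is not a new event.
- The SAE definition includes an event that "requires inpatient hospitalisation or prolongation of existing hospitalisation", but it governs safety reporting and does not define this endpoint.
- A reader might infer that many participants start as inpatients. The documents do not show this. Protocol 6.1.1 has patients identified through clinic visits, up to 28 days may separate screening from baseline, and treatment for an opportunistic infection may already have ended before ART.
- A reader might put a percentage on the days lost. Any such figure would only return the assumed inpatient share and remaining stay, and a share of days does not translate into a Kaplan-Meier median or its hazard ratio.
- Early treatment effects are not lost altogether. IRIS on study is counted in SAP 7.2.7 wherever the patient was, and adverse events in section 8.

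What the reply does not remove is that the result for one patient changes with an unstated choice, and that the SAP's clock and analysis set differ from the protocol's under either reading.

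**Conclusion.** The point holds as a gap in SAP 7.2.9 together with a departure from protocol 9.3.3. Under the admission-date reading, post-randomisation days of a stay ongoing at first dose are discarded, and a patient without a later admission drops out of the analysis.

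The size for the trial is unknown because the number of inpatients at first dose is not given. The per-patient figures above rest on assumed dates and show only that the reading matters.

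A reader might infer that the exclusion favours one arm. The documents do not support that: inpatient status at day 0 precedes randomised treatment, so exclusion on it alone should balance in expectation. The effect is on the scope, precision and protocol agreement of one secondary endpoint. The primary endpoint and the non-inferiority conclusion are untouched.

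**What to change.** In SAP 7.2.9, define duration as inpatient days from the date of first dose to week 48 in all mITT participants, with zero for those never in hospital. Include the remaining days of a stay ongoing at first dose, and exclude only days before it. Compare arms by Mann-Whitney, as in protocol 9.3.3. Use the same derivation for total inpatient days in SAP 10.1.2.

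Leave SAP 7.2.8 as time to first new admission after first dose, say so in its wording, and tabulate by arm how many participants were inpatients at first dose.

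The cost is SAP wording and one derivation. SAP 5.1 allows updates before sign-off. Discharge dates for stays ongoing at first dose may need data queries to sites. One limit remains, shared with the protocol's measure: participants who die or leave early have less time to accrue days, so follow-up time should be reported by arm beside the result.

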	Discontinued for lack of efficacy						
	Change in background therapy						
	No virologic data						
	Discontinuation due to AE/SAE						
	Discontinuation due for other reason						
	On study but missing data in window						
W36	HIV-RNA < 50 copies/mL						
	HIV-RNA ≥ 50 copies/mL						
	Data in window not below 50 copies/mL						
	Discontinued for lack of efficacy						
	Change in background therapy						
	No virologic data						
	Discontinuation due to AE/SAE						
	Discontinuation due for other reason						
	On study but missing data in window						
W48	HIV-RNA < 50 copies/mL						
	HIV-RNA ≥ 50 copies/mL						
	Data in window not below 50 copies/mL						
	Discontinued for lack of efficacy						
	Change in background therapy						
	No virologic data						
	Discontinuation due to AE/SAE						
	Discontinuation due for other reason						
	On study but missing data in window						

TABLE 4. OTHER SECONDARY EFFICACY ENDPOINTS

	Integrase Inhibitor	Protease Inhibitor	Adjusted Hazard ratio	P-value
	N=XXX	N=XXX		
Kaplan-Meier estimate of percentage of patients with CD4>200/ μ L, n (%)				
Kaplan-Meier estimate of median (95% CI) time to reach CD4>200/ μ L				
Kaplan Meier estimate of incidence of IRIS, n (%)				
Kaplan-Meier estimate of Incidence of hospitalisations, , n (%)				
Kaplan-Meier estimate of median (95% CI) duration of hospitalisation				

TABLE 5: EVOLUTION OF CD4 CELL COUNT <200/ μ L AND <350 AT WEEK 4, 8, 12, 24, 36 AND 48

Week	CD4 cell count <200/ μ L			CD4 cell count <350/ μ L		
	Integrase Inhibitor	Protease Inhibitor	P-value between groups	Integrase Inhibitor	Protease Inhibitor	P-value between groups
	n/N (%)	n/N (%)		n/N (%)	n/N (%)	
0						
4						
8						
12						
24						
36						
48						
RR (95% CI) from baseline to W4						
RR (95% CI) from baseline to W8						
RR (95% CI) from baseline to W12						
RR (95% CI) from baseline to W24						
RR (95% CI) from baseline to W36						
RR (95% CI) from baseline to W48						

TABLE 6: EVOLUTION OF CD4/CD8 RATIO AT WEEK 4, 8, 12, 24, 36 AND 48

Week	CD4/CD8 ratio		
	Integrase Inhibitor	Protease Inhibitor	P-value between groups
	Mean (SD)	Mean (SD)	
0			
4			
8			
12			
24			
36			
48			
Mean (95% CI) difference from baseline to week 4			
Mean (95% CI) difference from baseline to week 8			
Mean (95% CI) difference from baseline to week 12			
Mean (95% CI) difference from baseline to week 24			
Mean (95% CI) difference from baseline to week 36			

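### Censoring death in the Kaplan-Meier analysis of hospital discharge (SAP 7.2.9) overstates the proportion discharged and shortens the median stay whenever deaths precede later discharges

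*Combined protocol and SAP*

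**What the plan says.** SAP 7.2.9 analyses hospitalised patients in the mITT population, with time counted from first admission. It defines the event as follows: "The event of interest is the occurrence of last discharge (end date of hospitalisation) from hospital". It adds: "A transfer to a palliative care will not be considered a discharge". For estimation it says: "The proportion of participants discharged from hospital and the median duration of hospitalisation will be estimated using the Kaplan-Meier method". Follow-up is to "continue until the week 48 visit, study discontinuation or death, loss to follow-up, or last discharge from hospital; whichever occurs first". Death thus stands beside study discontinuation and loss to follow-up as a way of leaving the risk set without the event. The treatment effect comes from a Cox model adjusted for country group and baseline CD4.

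The section also plans crude counts: "Data will be summarized with the number and percentage of participants discharged from hospital, and the median (95% CI) duration of hospitalisation". The Table 4 shell has one row for this endpoint, "Kaplan-Meier estimate of median (95% CI) duration of hospitalisation", and none for the proportion discharged.

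Sections 7.2.7 and 7.2.8 are built the same way, with death ending follow-up: "The incidence of IRIS will be estimated with the Kaplan-Meier method" and "The incidence of hospitalisation will be estimated with the Kaplan-Meier method". No competing-risk estimator is named for any of the three. Protocol v5.0, section 9.3.3, plans something different for duration: total days in hospital, compared by a Mann-Whitney test.

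**The concern.** Kaplan-Meier assumes that a censored patient has the same future chance of the event as those still at risk. That can be defended for a patient lost to follow-up. It cannot hold for one who has died in hospital, because discharge is no longer possible. One minus Kaplan-Meier is then not a proportion of patients, although 7.2.9 calls it one.

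The SAP already declines to count a palliative transfer as a discharge, so it does not want a poor outcome read as a good one. Censoring death works against that intention. At stake are the discharge curve, the proportion read from it, and the tabulated median stay. If in-hospital mortality differs between arms, the two medians can be biased by different amounts.

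**Working it through.** **Inputs.** The documents give no number hospitalised, no in-hospital mortality and no expected proportion discharged, so there is no planned figure to reproduce. All rates below are assumptions, shown over a range. Two estimators are compared:

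- Kaplan-Meier (KM), death censored: 1 − product over discharge times of (1 − 1/number at risk).
- Aalen-Johansen (AJ), death competing. With no other censoring this is simply discharges so far divided by all patients.

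**Ten patients, one leaving on each of days 1 to 10.**

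- Deaths on days 2, 4, 6. KM: 1 − (9/10 × 7/8 × 5/6 × 3/4 × 2/3 × 1/2 × 0) = 100%. AJ: 7/10 = 70%. KM passes one half on day 7 (1 − 9/10 × 7/8 × 5/6 × 3/4 = 50.8%); AJ reaches it on day 8 (the fifth discharge).
- Deaths on days 2, 6, 10. KM: 1 − (9/10 × 7/8 × 6/7 × 5/6 × 3/4 × 2/3 × 1/2) = 85.9%, against 70%.
- Deaths on days 8, 9, 10. KM: 1 − (9/10 × 8/9 × ... × 3/4) = 1 − 3/10 = 70%, against 70%. There is no bias, because no discharge follows a death.

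**Simulated proportion discharged** (60 hospitalised patients, 2,000 runs per case, exponential stays with mean 14 days, week-48 censoring). Deaths are early (mean 7 days), spread like discharges, late (mean 28 days), or after all discharges:

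| Die in hospital | True discharged | KM, early | KM, like discharges | KM, late | KM, after all discharges |
|---|---|---|---|---|---|
| 5% | 95% | 100.0% | 99.9% | 99.3% | 95.0% |
| 10% | 90% | 100.0% | 99.7% | 98.2% | 89.9% |
| 20% | 80% | 100.0% | 99.2% | 94.9% | 80.1% |
| 40% | 60% | 99.8% | 96.4% | 82.7% | 60.0% |

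**Median stay, deaths spread like discharges.** With mean stay 14 days and mortality d, the discharge hazard is (1 − d)/14. The KM median is 14 × ln 2/(1 − d). The AJ median solves (1 − d)(1 − exp(−t/14)) = 0.5, so t = 14 × ln[(1 − d)/(0.5 − d)].

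- d = 5%: 10.2 against 10.5 days.
- d = 10%: 10.8 against 11.4 days.
- d = 20%: 14 × 0.693/0.8 = 12.1, against 14 × ln(0.8/0.3) = 13.7 days.
- d = 40%: 16.2 against 25.1 days.

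Simulated medians with 60 patients were close at the higher rates (12.1 and 14.1 at 20%; 16.3 and 25.5 at 40%). They depend somewhat on how a curve lying exactly at one half is read, so the closed form is the better guide.

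**IRIS and first hospitalisation.** Take constant hazards over 48 weeks, with a = −ln(1 − p) for the event and b = −ln(1 − q) for death. KM returns p; AJ returns a/(a + b) × [1 − (1 − p)(1 − q)].

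- p = 10%, q = 5%: 0.1054/(0.1054 + 0.0513) × 0.145 = 9.75%, an excess of 0.25 points.
- p = 10%, q = 2%: 0.1 point.
- p = 30%, q = 5%: 0.7 points.
- p = 30%, q = 10%: 1.4 points.

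**The case against.** A reader might infer that the reported proportion discharged will run to about 100% however many patients die. The documents do not support that. The curve reaches 100% only if the last patient at risk is discharged. If the longest stays end in death or week-48 censoring it stops lower, and keeping palliative transfers in the risk set makes such endings more likely. At 20% mortality the range above runs from 100% down to the true 80%.

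Other objections carry weight:

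- Section 7.2.9 also plans the crude percentage discharged, which does not have this bias, and Table 4 shows no Kaplan-Meier proportion. But the curve, the stated estimator of the proportion and the Table 4 median remain affected, and the report could carry two conflicting proportions.
- A reader might also infer that the treatment comparison is invalid, or that the arm with more deaths will look better. The comparison is a Cox model, and with death censored it gives a valid cause-specific hazard ratio for discharge. No two-arm case was worked, so distortion between arms is a possibility and has not been shown.
- Deaths are not hidden. HIV-related, infection-related and therapy-related deaths enter the primary endpoint, and Table 7 reports death by arm.
- For 7.2.7 and 7.2.8 the effect is small. SAP section 4 cites 12.2% per year for all severe morbidity together in the boosted PI arm, so the higher rates tried are generous.

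**Conclusion.** The point stands for the Kaplan-Meier proportion and median in SAP 7.2.9. Both are biased if any patient dies in hospital before later discharges occur; the median moves only through deaths that precede it. At an assumed 20% in-hospital mortality spread like discharges, the proportion is about 99% against 80% and the median about 12 against 14 days. At 5% the median shifts by about a quarter of a day, though the proportion still reads 99.9% against 95%. The size depends on how many die and when, neither of which the documents give.

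The crude percentage and the Cox models are sound. In 7.2.7 and 7.2.8 the overstatement is about 0.1 to 1.4 points under the rates tried, so a change there is for consistency. These are secondary endpoints and the primary conclusion does not change. It should be corrected because a tabulated result is affected and the remedy is cheap.

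**What to change.** In 7.2.9 and the Table 4 duration row, replace Kaplan-Meier by the Aalen-Johansen cumulative incidence of discharge alive, with death as the competing event; other reasons for leaving follow-up stay censored. Take the median from that curve, say how its 95% CI is obtained, and report it as not reached if the curve stays below one half. By arm, report the number and proportion discharged alive and the number and proportion who died before last discharge. That wording also settles deaths during a later stay, since time runs from first admission to last discharge.

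Label the Cox hazard ratios cause-specific. Use the same estimator in 7.2.7 and 7.2.8 and their Table 4 rows for consistency. An adjusted hazard ratio for in-hospital death is not needed and would rest on very few events.

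The cost is SAP wording and a small programming change. The estimator is standard in the named software, no new data are required, and SAP 5.1 allows updates before sign-off.
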